5. AMENDMENTS AND UPDATES

Amendment number	Date	Protocol section(s) changed	Summary of amendment(s)	Reason
Amendment 1 (V.2.0)	28Mar2022	Study information	Changed index treatment grouping to PAC only, warfarin-based, and NOAC-based therapy.	Amendment following Protocol Administrative Change Letter in Oct 22, 2021
			Updated author information	Revised due to author's title change
		4. Abstract	Changed index treatment grouping to PAC only, warfarin-based, and NOAC-based therapy.	Amendment following Protocol Administrative Change Letter in Oct 22, 2021
			Added secondary objective of Phase I	Revised according to additional analysis in Phase I
			Added outcome for secondary objective of Phase I	
			Revised data analysis for additional analyses	
		6. Milestones	Updated planned dates to study milestones	Revised due to change in study schedule
		8. Research question and objectives	Added secondary objective of Phase I	Revised according to additional analysis in Phase I
		9.1 Study design	Updated Figure 1 and Figure 2	Amendment following Protocol Administrative Change Letter in Oct 22, 2021
		9.3 Variables	Revised the sentence regarding heparin bridging period	Amendment following Protocol Administrative Change Letter in Oct 22, 2021 (acute heparin therapy to be considered in all OACs)
			Added outcome definition for secondary objective of Phase I	Added according to additional analysis in Phase I
			Revised evaluation period of comorbidities (APS, history of cancer)	Amendment following Protocol Administrative Change Letter in Oct 22, 2021 and detailed explanation
			Added antiplatelet agents and azole antifungal agents	
		9.7 Data analysis	Added data analysis for secondary objective of Phase I	Revised according to additional analysis in Phase I

PFIZER CONFIDENTIAL

6. MILESTONES

Milestone [†]	Planned date
Institutional Review Board (IRB) approval	1Q 2021
HIRA data application	1Q 2021
Study protocol development	1Q 2021
Study protocol finalization and approval	2Q 2021
HIRA data extraction and access	2Q 2021
Data analysis	3Q 2021
Preliminary results	3Q 2021
Data analysis for final	2Q 2022
Manuscript draft	2Q 2022
Final study report	3Q 2022
Manuscript finalization and approval	3Q 2022

[†]Note that milestones are dependent on timely delivery of data provided by HIRA

7. RATIONALE AND BACKGROUND

Venous thromboembolism (VTE) is a disorder that includes deep vein thrombosis (DVT) and pulmonary embolism (PE). Of VTE, DVT occurs when a blood clot forms in a deep vein, usually in the lower leg, thigh, or pelvis and PE occurs when a clot breaks loose and travels through the bloodstream to the lungs to eventually block an artery in the lung. Blood clots can develop in veins when damaged by surgery or trauma, or because of an inflammation in response to an infection or injury. Other risk factors for VTE include a history of a previous VTE event, comorbidities such as cancer or spinal cord injury, pregnancy, paralysis or long periods of immobilization, specific genes, and certain circumstances related to age, race, and sex. As a previous VTE event is a strong risk factor for the onset of VTE, recurrence of VTE is common, with a previous study reporting that approximately 30% of patients who experienced VTE will develop recurrent VTE within 10 years of their initial event [1]. With high rates of recurrence and mortality, as well as increased long-term morbidity and functional disability, VTE remains a major public health concern with a substantial disease burden [2] [3].

For pharmacologic treatment of patients with VTE without cancer, the American College of Chest Physicians (CHEST) guidelines recommend the use of non-vitamin K antagonist oral

anticoagulants (NOACs) over Vitamin K Antagonists (VKAs), with supporting evidence suggesting that each NOAC (e.g., apixaban) is effective at preventing recurrent VTE [4]. More recently, in the treatment guidelines for management of VTE released by the American Society of Hematology (ASH), NOACs are still recommended over VKAs for the initial management of VTE [5].

NOACs, or also known as direct oral anticoagulants (DOACs), are a relatively new generation of anticoagulants approved by the US FDA; dabigatran, rivaroxaban, apixaban, and edoxaban were approved in October 2010, July 2011, December 2012, and January 2015, respectively, for treatment indication of risk reduction of stroke and embolism in nonvalvular atrial fibrillation (NVAF) [6]. These NOACs have also been approved for prophylaxis and treatment of DVT and PE, which comprise VTE [7, 8]. Compared with VKAs, NOACs have fewer drug interactions, food interactions, and adverse effects and therefore, do not require frequent laboratory monitoring or dosage adjustments [4, 9]. Among NOACs, apixaban and rivaroxaban were approved as a single-drug approach for the treatment of VTE and do not require initial parenteral treatment with low molecular weight heparin (LMWH) or unfractionated heparin (UFH) [10, 11]. In actual real-world clinical practice, the two aforementioned NOACs are the most widely used and preferred treatments for VTE and preventing its recurrence [12-14]. Although NOACs demonstrated better safety profile than VKAs, concerns regarding their risk of adverse bleeding events remain due to their mechanism of action [15].

With both conventional and new anticoagulant therapies being used in real-world clinical practice, it is necessary to identify the utilization characteristics of individual anticoagulant treatments through the analysis of nationwide claims database. It is important to examine the treatment pattern and assess whether Korean patients are being treated appropriately based on the current treatment guidelines.

Several previous studies evaluated comparative effectiveness and safety of apixaban versus warfarin in patients with VTE. According to the AMPLIFY trial, the use of apixaban was non-inferior to conventional therapy for the treatment of VTE (relative risk [RR] 0.84, 95% confidence interval [CI] 0.60-1.18) and was superior to the bleeding event (RR 0.44, 95% CI 0.36-0.55) [10]. In the same manner as the results of the clinical trial, pharmacoepidemiologic studies reflecting real-world practice showed consistent results [16, 17]. However, those studies were focused on the western population, and the evidence on the effectiveness and safety of warfarin and apixaban from real-world clinical practice among the Asian population with venous thromboembolism is still limited. Of the NOACs, both apixaban and rivaroxaban are known to have low rates of major bleeding events [18, 19]. One US population-based retrospective cohort study compared the risk of major bleeding events between apixaban and rivaroxaban in patients with VTE [20]. According to the study's findings, the use of apixaban was associated with a reduced risk of major bleeding events when compared to rivaroxaban use (hazard ratio [HR] 0.54, 95% confidence interval [CI] 0.37-0.82). Although findings suggest a significant protective effect on major bleeding events associated with apixaban, more studies are needed to provide evidence on the different risk of major bleeding events between apixaban and other OACs in various ethnic populations.

Therefore, through this retrospective study utilizing Korean national claims database, we aim to 1) describe the clinical characteristics and anticoagulant treatment pattern of Korean VTE patients and 2) evaluate the safety outcome of current anticoagulant therapy regarding bleeding.

8. RESEARCH QUESTION AND OBJECTIVES

Research Question

What is the real-world evidence of anticoagulant treatment for patients with VTE that can be found in the nationwide claims database in Korea? The current study will take place in two phases:

Phase I involves a descriptive assessment of patient characteristics and treatment patterns in Korea as well as detailed power calculations for comparative study.

Phase II involves analyses of comparative safety between each NOAC and warfarin. These analyses will be implemented if there is sufficient power to enable scientifically valid inferences.

Primary Objectives of Phase I of the study

- To describe the sociodemographic and clinical characteristics of patients with VTE, overall and according to their index VTE treatment (PAC only, warfarin-based, NOAC-based)
- To describe index anticoagulant treatment patterns by investigating the utilization of different anticoagulants, treatment interruption, switches, discontinuations, and overall treatment duration

Primary Objective of Phase II of the study

- To describe and compare the risk of clinical outcome (major bleeding) according to the specific type of OAC

[NOTE] Comparative analyses, especially NOAC vs NOAC direct comparisons, will be performed contingent on a feasibility assessment based on the descriptive analyses and agreed opinion on scope after discussion with Eliquis Alliance Real World Data Review Committee.

Secondary objective of Phase I of the study

- To explore the relevant clinical events preceding treatment change from index anticoagulant

9. RESEARCH METHODS

9.1. Study design

A retrospective, observational, nationwide population-based cohort study will be conducted to describe the treatment patterns of anticoagulation therapies prescribed to patients with VTE in South Korea, and assess the risk of major bleeding associated with apixaban and other NOACs use, as compared with warfarin, by using the Health Insurance Review and Assessment Service (HIRA) database from 1 Mar 2012 to 31 Dec 2019 (Figure 1).

[figure not shown]

Figure 1. Study participants inclusion and exclusion criteria

Note: HIRA, Health Insurance and Review Assessment service; LMWH, low molecular weight heparin; NOAC, non-vitamin K antagonist; PAC, parenteral anticoagulants; VTE, venous thromboembolism

[†]Record of active cancer is defined as first diagnosis of cancer with V code within the past 6 months of period prior to index date; or receiving anti-cancer treatment under cancer diagnosis with V code within the past 6-month period prior to index date.

[‡]Warfarin-based and NOAC-based include either PAC with warfarin/NOAC or warfarin/NOAC only.

The study cohort will be defined as patients diagnosed with VTE between 1 Mar 2013 and 30 Jun 2019. The cohort entry will be defined as the date of incident VTE diagnosis. The index date will be defined as the date of first prescription for anticoagulants within 30 days after the index VTE event. The length of the exclusion assessment window will vary depending on the condition, from 12-months at minimum to anytime prior to index date. The following patients will be excluded: A record of VTE diagnosis within the 12-month period prior to the index VTE encounter, diagnosed with atrial fibrillation, atrial flutter, mechanical heart valve replacement or mitral stenosis anytime prior to index date, had a record of Inferior Vena Cava filter anytime prior to index date, received anticoagulatory therapy within the 12-month period prior to index VTE encounter to restrict to new users of anticoagulatory therapy, prescribed two different anticoagulants on the same index date to prevent exposure misclassification, had a record of pregnancy within the 9-month period prior to index date, and for the Phase II of the study only, had a record of active cancer within six months period prior to index date.

Baseline sociodemographic characteristics (e.g., age, sex) will be assessed on the index date, whereas clinical characteristics (comorbidities, previous use of medications, Charlson comorbidity index [CCI], HAS-BLED scores, initial presentation of VTE, number of outpatient visits) will be assessed in the 6-month period prior to the index date except when otherwise specified in section 9.3 *Variables* (Figure 2).

[figure not shown]

Figure 2. Overall study schematic

- Baseline conditions included: Charlson comorbidity index, HAS-BLED scores, comorbidities (antiphospholipid syndrome, asthma, cancer, chronic obstructive pulmonary disease, chronic kidney disease, chronic liver disease, diabetes mellitus, fracture, heart failure, hyperlipidemia, hypertension, ischemic heart disease, myocardial infarction, stroke, trauma), previous use of medications (corticosteroids, nonsteroidal anti-inflammatory drugs, angiotensin-converting enzyme inhibitors,

- angiotensin II receptor blockers, antiplatelet agents, azole antifungal agents, β -blockers, calcium-channel blockers, selective serotonin reuptake inhibitors, proton pump inhibitors, diuretics, thiazides, vasodilators, estrogens, cyclooxygenase-2 inhibitors), initial presentation of VTE (DVT, PE, both DVT and PE), number of outpatient visits
- b. Earliest of: outcome of interest (major bleeding event), treatment discontinuation, switch to another anticoagulant, in-hospital death, end of the study period (31 Dec 2019)

Note: Dx, diagnosis; NOAC, non-vitamin K antagonist oral anticoagulant; Rx, prescription; VTE, venous thromboembolism; PE, pulmonary embolism

Within this study cohort, we will describe the treatment patterns of anticoagulants prescribed for VTE treatment throughout the period of follow-up, defined as the period from the index date to the end of the study period. Moreover, if feasible, we will also examine the risk of major bleeding overall and by site, associated with each NOAC use, as compared with warfarin.

9.2. Setting

9.2.1. Inclusion criteria

Patients must meet all of the following inclusion criteria to be eligible for inclusion in the study:

1. Incident VTE diagnosis in an inpatient or outpatient setting (International Classification of Diseases 10th Revision [ICD-10]: I26.0, I26.9, I80.2, I80.3) between 1 Mar 2013 and 30 Jun 2019
2. Received anticoagulation therapy (all medication codes for anticoagulants approved for VTE in Korea; UFH, LMWH, warfarin, and NOACs) within 30 days of their VTE diagnosis (the index date will be defined as the date of treatment initiation with anticoagulants)
3. Aged ≥ 18 years at index date

9.2.2. Exclusion criteria

Patients meeting any of the following criteria will not be included in the study:

1. Had a record of VTE diagnosis (ICD-10: I26.0, I26.9, I80.2, I80.3) within the 12-month period prior to the index VTE encounter.
2. Diagnosed with atrial fibrillation/flutter (ICD-10: I48), mechanical heart valve replacement (National Procedure Code: Z952, M6531, M6532, M6533, O1781, O1782,

O1783, O1791, O1792, O1793, O1797, O1794, O1795, O1796, O1798, O1799) or mitral stenosis (ICD-10: I05.0, I05.2) anytime prior to index date

3. Had a record of Inferior Vena Cava filter (National Procedure Code: O2045, M6650) anytime prior to index date
4. Received anticoagulatory therapy within the 12-month period prior to index VTE encounter to restrict to new users of anticoagulatory therapy.
5. Prescribed two different anticoagulants on the same index date to prevent exposure misclassification.
6. Had a record of pregnancy (ICD-10: O03-O07, O10-O14, O16, O20-O026, O28-O36, O41-O43, O46.8, O46.9, O61-O66, O67.8, O67.9, O69, O70-O75, O80-O92, O94-O99, P08, Z33-Z39) within the 9-month period prior to index date
7. Had a record of active cancer, defined as first diagnosis of cancer (ICD-10: C00-C97 [excluding non-melanoma skin cancer: C44]) with V code (V011, V027, V193, V194; a special code applied to patients with confirmed diagnosis of cancer by Korean Ministry of Health and Welfare for reimbursement for 5 years or longer if recurrent/metastasis) within the past 6 months of period prior to index date; or receiving anti-cancer treatment (chemotherapy, radiation therapy, or cancer-related surgery) under cancer diagnosis with V code within the past 6 months from index date (for Phase II of the study only). WHO-ATC codes and National Procedure Codes for anti-cancer treatment are shown in Table 1.

Table 1. WHO-ATC codes and National Procedure Codes for anti-cancer treatment

Anti-cancer treatment	WHO-ATC codes / National Procedure Codes
Chemotherapy	L01-04, H02AB02, H02AB04, H02AB06, H02AB07, H02AB09
Radiation therapy	HD051-HD059, HD061, HD071-HD073, HD080-HD089, HD091-HD093, HD110-HD115, HD121, HD150, HD160, HD211, HD212, HZ271
Cancer-related surgery	N0232, N0284-N0286, NA281-NA284, N0335, N0404, N0405, N0435-N0437, N0940, O0961-O0963, O1045, O1047, O1048, O1224-O1227, O1251, O1252, O1401, O1403-O1405, O1410, O1421-O1424, O1431, O1432, O1471, O1484, O1486, O1572, O1592, O1596, O1982, P2091, P2093, P2123, P2124, Q2150, Q2181-Q2183, Q2203, Q2206, Q2232, Q2292-Q2294, Q2346, Q2347, Q2348, Q2361, Q2362, Q2363, Q2365-Q2369, Q2401, Q2402, Q2403, Q2502, QA536, Q2533, Q2534, Q2536, Q2537, Q0251-Q0259, Q2594, Q2598, Q2601, Q2650,

PFIZER CONFIDENTIAL

	Q2651, QA671-QA673, QA679, Q1261, Q1262, Q2671-Q2673, Q2679, Q2761, Q2762, Q2791-Q2794, Q2796-Q2798, Q2890-Q2893, Q2901, Q0292, Q2921-Q2924, Q2927, Q2928, QA921-QA924, QA928, Q2925, Q2926, QA925, QA926, R3271, R3273, R3274, R3275, R3290, R3305, R3307, R3299, R3300, R3309, R3310, R3432, R3433, R3451, R3470, R3481, R3482, R3541-R3543, R3530, R3590, R3755, R3756, R3791, R3792, R3801, R3802, R3851, R3853, R3861, R3862, R3891, R3901, R3902, R3950, RZ512, R3960, R3975, R4003, R4004, R4067, R4068, R4071-R4074, R4140, R4143, R4144, R4147-R4149, R0141, R0142, R4154, R4155, R4156, R4250, R4331, R4332, R4423-R4428, P4543, P4551-P4554, P4561, P4571, P4572, S4616, S4634-S4639, S6691-6696, S4694-S4696, S4707-S4709, S4743, S4756-S4758, S4780, S4801-S4803, S4880, S4900, S4950, S5200, S5220, S5231, S5232, S5246, S5592, S5745, M6774, M6870, M6880, M6775, QZ841, M6890, M6900, M6991, M6910, Q0841, Q0842, N7136-N7139, N7140-N7153, Q7221-Q7225, Q7230, Q7280-Q7285, Q7342, Q7380, Q7410, Q7561-Q7567, Q7571, Q7572, Q7651-Q7654, Q7701-Q7703, QX706, Q7751, Q7752, Q7761-Q7763, Q7766, Q7771, Q7772, Q7775, Q7788, Q7789, U4811, U4812, U4881-U4883
Others	X5131-X5137 (hemopoietic cell transplantation)

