9.3. Variables

Exposure

- **Phase I of the study:** PAC (UFH [Anatomical Therapeutic Chemical [ATC] code: B01AB01], LMWH [B01AB04, B01AB05, B01AB06, B01AB12]), VKA (warfarin [B01AA03]), NOACs (apixaban [B01AF02], rivaroxaban [B01AF01], edoxaban [B01AF03], dabigatran [B01AE07])
- **Phase II of the study:** Apixaban (B01AF02), Rivaroxaban (B01AF01), Edoxaban (B01AF03), Dabigatran (B01AE07), Warfarin (B01AA03)

Outcome(s)

- **Phase I of the study**

- Sociodemographic and clinical characteristics of patients with VTE who initiated anticoagulants.
- Utilization of different anticoagulants at treatment initiation. Patients will be classified based on their index anticoagulant treatment received within 30 days after being diagnosed with VTE.
- Treatment interruption from the index anticoagulant treatment, which will be defined as when a patient has a gap with no new treatment within 30 days of the estimated end of supply, but subsequently restarts the index treatment after this period.[21] The time to treatment interruption will be defined as the period from the index date to the date of treatment interruption.
- Treatment switching will be defined as a prescription of another anticoagulant therapy that is started after the treatment initiation of the index anticoagulant treatment and within 30 days after the estimated end of supply of the index anticoagulant drug (exposure to the new anticoagulant treatment must last for at least 30 days to be considered as a treatment switch). The time to treatment switch will be defined as the period from the index date to the date of treatment switch.

Exemption: As heparin can be initiated at acute stage of DVT/PE before clinical decision to use OAC, a switch from initial heparin treatment to an OAC within 2 weeks after heparin treatment initiation will not be considered a treatment switch.

- Treatment discontinuation (complete discontinuation; no reinitiation) will be defined as when a patient who ended their first continuous treatment episode with the index anticoagulant treatment without switching, and subsequently have no further prescriptions for that respective anticoagulant treatment during all available follow-up time. The time to treatment discontinuation will be defined as the period from the index date to the date of treatment discontinuation.

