9.7. Data analysis

Phase I of the study (descriptive)

Main Analysis

PFIZER CONFIDENTIAL

- Descriptive analysis will be conducted separately in two cohorts of non-cancer VTE and cancer VTE patients according to co-presence of active cancer.
- Sociodemographic and clinical characteristics will be summarized with means (standard deviations [STD]) or median (interquartile range [IQR]) for continuous variables and with count (proportions) for categorical variables for the three treatment groups of interest: PAC only (UFH, LMWH, UFH+LMWH), warfarin-based (warfarin, PAC/warfarin) group, NOAC-based (NOAC, PAC/NOAC) group. Analysis of variance, and chi-square test will be conducted for continuous variables, and categorical variables, respectively.
 - In order to distinguish between PAC bridging therapy and PAC treatment, we will apply a time restriction of 2 weeks to PAC bridging therapy.
- Temporal trend in anticoagulation therapy for VTE will be presented between 1 Mar 2013 and 30 Jun 2019. Proportions of the index OACs will be estimated according to calendar year and quarter.
- The number and percentage of patients who discontinue treatment completely, experience treatment interruption and treatment switch during their follow-up will be described by the index anticoagulant treatment received. Results will be limited to the first of each of these events for each patient. For patients experiencing a treatment switch, the new treatment will be described at the time of their first switcher per individual drug.
- The duration of the index treatment by the index anticoagulant treatment received will also be summarized in terms of days using descriptive statistics (mean [STD], median [IQR]).
- The Kaplan-Meier method will be applied to derive the empirical distribution of time to each of the treatment endpoints of interest (e.g., treatment discontinuation or switch); these analyses will be performed per index anticoagulant treatment received and no comparisons will be made. Log-rank test will be conducted at the 3-, and 6 months after treatment initiation to assess statistical significance between the survival curves among three treatment groups of interest. Persistent rate will also be calculated at the same time point.

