Table 18. Risk of major bleeding events by site, intracranial, gastrointestinal, all others, associated with NOAC use versus warfarin

	No of Patients	No of Events	Person-years	Incidence rate* (95% CI)	Crude HR (95% CI)	IPT-Weighted HR (95% CI)
Intracranial bleeding						
Warfarin-based						Reference (1.00)
Apixaban						
Rivaroxaban						
Edoxaban						
Dabigatran						
Gastrointestinal bleeding						
Warfarin-based						Reference (1.00)
Apixaban						
Rivaroxaban						
Edoxaban						
Dabigatran						
All other sites						
Warfarin-based						Reference (1.00)
Apixaban						
Rivaroxaban						
Edoxaban						
Dabigatran						

Note: CI, confidence interval; HR, hazard ratio; IPT, inverse probability of treatment.

*Events per 1000 person years.

Table 19. Subgroup analyses for the risk of major bleeding events associated with NOAC use versus warfarin

	No. of Patients	No. of Events	IPT-Weighted HR (95% CI)	P _{interaction} *
Age				
<65 years				
Warfarin-based			Reference (1.00)	
Apixaban				
Rivaroxaban				
Edoxaban				
Dabigatran				
≥65 years				
Warfarin-based			Reference (1.00)	
Apixaban				
Rivaroxaban				
Edoxaban				
Dabigatran				
Sex				
Female				
Warfarin-based			Reference (1.00)	
Apixaban				
Rivaroxaban				
Edoxaban				
Dabigatran				
Male				
Warfarin-based			Reference (1.00)	
Apixaban				
Rivaroxaban				
Edoxaban				
Dabigatran				
VTE diagnosis setting				
Inpatient				
Warfarin-based			Reference (1.00)	
Apixaban				
Rivaroxaban				
Edoxaban				
Dabigatran				
Outpatient				
Warfarin-based			Reference (1.00)	
Apixaban				
Rivaroxaban				
Edoxaban				
Dabigatran				
Type of VTE				
DVT without PE				
Warfarin-based			Reference (1.00)	

Apixaban

Rivaroxaban

Edoxaban

Dabigatran

PE with or without DVT

Warfarin-based

Reference (1.00)

Apixaban

Rivaroxaban

Edoxaban

Dabigatran

VTE etiology

Major orthopedic

surgery-provoked VTE

Warfarin-based

Reference (1.00)

Apixaban

Rivaroxaban

Edoxaban

Dabigatran

Chronic kidney disease

With CKD stage 3 or 4

Warfarin-based

Reference (1.00)

Apixaban

Rivaroxaban

Edoxaban

Dabigatran

Without CKD stage 3 or 4

Warfarin-based

Reference (1.00)

Apixaban

Rivaroxaban

Edoxaban

Dabigatran

Note: CI, confidence interval; DVT, deep vein thrombosis; HR, hazard ratio; IPT, inverse probability of treatment; PE, pulmonaryembolism; VTE, venous thromboembolism

*P for interaction will be calculated between warfarin-based therapy and each NOAC.

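### Exclusion 5 as worded removes same-day heparin plus one OAC and same-day UFH plus LMWH, which the amended treatment groups are defined to include

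*Protocol*

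**What the plan says.** Exclusion 5 in Protocol 9.2.2 reads "Prescribed two different anticoagulants on the same index date to prevent exposure misclassification". The same rule appears in the Protocol abstract, Protocol 9.1, SAP 8.2 and SAP 8.3.2. It carries no phase restriction; only exclusion 7 is limited to Phase II.

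Inclusion 2 (Protocol 9.2.1) sets the scope of the word anticoagulant: "all medication codes for anticoagulants approved for VTE in Korea; UFH, LMWH, warfarin, and NOACs". The index date follows the same scope (Protocol 9.1): "The index date will be defined as the date of first prescription for anticoagulants within 30 days after the index VTE event".

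The amended grouping counts combinations as part of the groups. The Figure 1 footnote says "Warfarin-based and NOAC-based include either PAC with warfarin/NOAC or warfarin/NOAC only". Protocol 9.7, matched in SAP 10, lists "PAC only (UFH, LMWH, UFH+LMWH), warfarin-based (warfarin, PAC/warfarin) group, NOAC-based (NOAC, PAC/NOAC) group".

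Two further rules concern heparin. Protocol 9.3 says "a switch from initial heparin treatment to an OAC within 2 weeks after heparin treatment initiation will not be considered a treatment switch". Protocol 9.7 says "we will apply a time restriction of 2 weeks to PAC bridging therapy".

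**The concern.** The eligibility rule and the grouping use the same drug list but treat a shared prescription date differently. A patient with heparin and one OAC belongs to a named group if the OAC starts a day later, and is not in the study if both start together. UFH and LMWH behave the same way.

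The stated purpose, avoiding exposure misclassification, is served for two OACs on one day, because no group can be assigned. It is not served for PAC plus a single OAC, or for UFH plus LMWH, because the plan already assigns those.

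Phase I describes patients and treatment patterns by index treatment, and index OAC shares by calendar year and quarter. Those descriptions would omit part of what they are meant to describe. In Phase II, SAP Tables 13 to 20 use the warfarin-based group as comparator, and the Table 19 note confirms it: "P for interaction will be calculated between warfarin-based therapy and each NOAC". Protocol 7 says apixaban and rivaroxaban do not require initial parenteral treatment, so the loss could differ between drugs. That is an inference; nothing in the documents measures it.

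**Working it through.** **1. Apply the text to simple cases.**

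| Prescriptions | Exclusion 5 as written | Group under Protocol 9.7 |
|---|---|---|
| Heparin day 0, warfarin day 1 | kept | warfarin-based |
| Heparin and warfarin day 0 | excluded | warfarin-based, if eligible |
| Heparin day 0, NOAC day 1 | kept | NOAC-based |
| Heparin and NOAC day 0 | excluded | NOAC-based, if eligible |
| UFH day 0, LMWH day 1 | kept | PAC only |
| UFH and LMWH day 0 | excluded | PAC only, if eligible |
| Warfarin and NOAC day 0 | excluded | none assigned |

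Only the last row needs exclusion 5.

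**2. Look for a rule that restores eligibility.** The 9.3 exemption defines what is not a switch. The 2-week rule in 9.7 separates bridging from PAC treatment. Both act on patients already in the cohort. The amendment logs record the regrouping but list no change to Protocol 9.2 or SAP 8.3, and the current criteria contain no exception.

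**3. How large a loss would matter for power?** No same-day share is given, so these are break-even points on assumed losses. They take the projected counts in Protocol 9.5 as made before exclusion 5; the section does not say whether the rule was applied to the 2018 sample.

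Inputs from Protocol 9.5 (event probability p, counts over 7 years):
- Apixaban 19,362, warfarin 29,862; p = 1.19%; HR 0.75
- Dabigatran 6,062, warfarin 30,093; p = 1.4%; HR 0.69
- Edoxaban 13,300, warfarin 29,624; p = 8.5%; HR 0.81
- Rivaroxaban 61,593, warfarin 27,531; p = 8.1%; HR 1.19

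Schoenfeld formula, with q the NOAC share and N the total: N for 80% power = (1.960 + 0.842)² / [(ln HR)² q(1−q) p], where (1.960 + 0.842)² is taken as 7.849 (unrounded).

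Reproducing the plan:
- Apixaban: q = 19,362/49,224 = 0.393; 7.849/(0.0828 × 0.2386) = 397.4 events; /0.0119 = 33,398 (stated 33,340).
- Dabigatran: q = 6,062/36,155 = 0.168; 7.849/(0.1377 × 0.1396) = 408.5 events; /0.014 = 29,177 (stated 29,071).

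Power = Φ(|ln HR| √[N p q(1−q)] − 1.960):
- Apixaban: Φ(3.401 − 1.960) = 92.5%.
- Dabigatran: Φ(3.119 − 1.960) = 87.7%.

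With an equal proportional loss f in both arms the first term is multiplied by √(1−f):

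| Equal loss | Apixaban, HR 0.75 | Dabigatran, HR 0.69 |
|---|---|---|
| 0% | 92.5% | 87.7% |
| 5% | 91.2% | 86.0% |
| 10% | 89.7% | 84.1% |
| 20% | 86.0% | 79.7% |
| 30% | 81.2% | 74.2% |

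Break-even for 80% power, equal loss = 1 − (required N / projected N):
- Apixaban: 1 − 33,398/49,224 = 32.2%
- Dabigatran: 1 − 29,177/36,155 = 19.3%
- Edoxaban: 1 − 9,725/42,924 = 77.3%
- Rivaroxaban: 1 − 15,000/89,124 = 83.2%

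For loss in one arm, 80% power needs n₁n₂/(n₁+n₂) = 7.849/[(ln HR)² p], which is 7,970 for apixaban and 4,072 for dabigatran.
- Apixaban, warfarin-only loss: about 13,545 of 29,862 must remain, a 54.6% loss.
- Dabigatran, warfarin-only loss: about 12,402 of 30,093 must remain, a 58.8% loss.
- Dabigatran, dabigatran-only loss: about 4,709 of 6,062 must remain, a 22.3% loss.

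**4. Check on the baseline.** The inclusion window, March 2013 to June 2019, is 76 months, not 84. Scaling all counts by 76/84 lowers power to 89.9% for apixaban and 84.3% for dabigatran, and the equal-loss break-evens to about 25% and 11%.

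**The case against.** The rule can be read by its purpose. Since PAC plus one OAC already has a group, nothing is misclassified, so the rule may have been meant only for two conflicting index treatments. Figure 1, which depicts eligibility and was updated in the amendment, is not available to check. Even read literally, every named group can still be filled by sequential starts, so this may be a restrictive cohort choice applied consistently. No consequence is demonstrated. Phase II also proceeds only after a Phase I power and feasibility assessment, by which time any loss would already show in the counts.

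Much of this is fair, and it limits the claim. The groups are not emptied, the number affected is unknown, and the power gate guards against an underpowered Phase II. It does not remove the conflict. The purposive reading is not what the criterion says in any of its five places, and the documents write OACs elsewhere when they mean oral drugs only. If that reading is the intent, the remedy is to write it down. A figure cannot override the written criterion. The power gate does not return missing patients to the Phase I tables and trends, or to the comparator.

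**Conclusion.** The concern holds. As written, exclusion 5 removes from both phases patients whom the amended grouping places inside the study, on no basis other than a shared prescription date. Two programmers could build different cohorts from the same text.

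Its size cannot be determined. Shifts in treatment shares, in the make-up of the warfarin-based comparator or in power are possible, not shown. Power is a worry mainly for dabigatran vs warfarin at HR 0.69, and only if the loss is substantial: about 19% of both arms on the plan's projections, or about 11% after allowing for the 76-month window. These thresholds assume that the projections were made before exclusion 5, that the event probability stays fixed, and that the Schoenfeld approximation applies without allowance for weighting.

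**What to change.** In Protocol 9.2.2 and SAP 8.3.2, and in the copies in the Protocol abstract, Protocol 9.1 and SAP 8.2, limit exclusion 5 to patients prescribed two different oral anticoagulants on the index date. State that same-day PAC plus one OAC is classified in that OAC's group and same-day UFH plus LMWH in PAC only. Report how many patients the rule excludes, by drug, and say whether it was applied to the 2018 sample counts.

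The cost is a short amendment to each document and a code change, with no new data. Patients given two OACs on one day stay excluded. The milestones place preliminary results in 3Q 2021, before version 2.0 of April 2022. If the Phase I cohort was already built under the literal rule, it would have to be rebuilt and its tables rerun, and the report should say that the change came after preliminary results.
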